3.1.2. Secondary Endpoints

- The percentage of patients testing negative for blood in stool by Study Day 7, 14 and 28 by hemoccult testing
- The percentage of patients with no gross/visible blood in stool by Study Day 7, 14 and 28 by parental report
- Changes to stool frequency by Study Day 7, 14 and 28
- Changes to clinical symptoms including GER, feeding difficulties, sleep disturbance and poor growth
- The occurrence of supplement-related adverse events

3.1.3 Biomarkers / Exploratory Endpoints:

- Fecal calprotectin levels
- Fecal pH levels
- Fecal metabolomics
- Markers of inflammation and enteric cytokines including, but not limited to, IL-1, IL-8 and TNF-alpha in stool
- Levels of eosinophil-related granular proteins in stool
- Intestinal permeability/integrity markers including, but not limited to, lipocalin (NGAL)

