6.3.1.2 Secondary Objectives

The secondary objectives of this study are to evaluate: clinical symptoms including blood in stool, stool frequency, GER, feeding difficulties, sleep disturbance and poor growth

6.3.1.2.1 Blood in stool Blood in stool will be assessed by daily hemoccult stool test on Days 0, 1-14, 21 (+/- 1 day), 28 (+/- 1 day)

6.3.1.2.2 Stooling Infant stooling will be assessed by daily log capturing frequency, consistency, night stooling, and presence of mucus or gross blood

6.3.1.2.3 Infant GER Infant GER will be assessed by standard Reflux Questionnaire on Day 7, 14, 21, and 28

6.3.1.2.4 Infant Sleep Infant sleep duration/quality will be assessed by Questionnaire on Day 7, 14, 21, and 28

6.3.1.2.5 Infant Feeding Infant feeding difficulties will be assessed by Questionnaire on Day 7, 14, 21, and 28

6.3.1.2.6 Infant Growth Infant growth will be monitored at weekly visits by measuring weight, length, and head circumference

6.3.1.2.7 Adverse Events Supplement-related adverse events will be recorded by parents in a health log, in consultation with the study team and PI.

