6.3.2 Safety and Other Exploratory Assessments

Safety assessments will include parent-reported adverse events as described in Section 10.2.

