10.2.2 Collecting, Recording and Managing Adverse Events

10.2.2.1 Identifying Adverse Events Any adverse event that occurs from the moment the participant has signed the consent form will be recorded and is reportable. Adverse events will be reported until the participant has completed the long-term follow-up phase.

Adverse events may be discovered through any of these methods:

- Observing the participant.
- Questioning the participant with standardized questions/procedures.
- Receiving an unsolicited complaint from the participant.
- An abnormal value or result from a clinical or laboratory evaluation (e.g., a radiograph, an ultrasound, or an electrocardiogram) can also indicate an adverse event.

Adverse events will be captured as follows: (1) every occurrence as per the NCI-CTCAE criteria, (2) for protocol-specific adverse events (Section 10.2.1.3) or (3) when determined to be clinically significant by the Principal Investigator.

All adverse events occurring during or within 24 hours of the study procedures will be reported as an adverse event.

10.2.2.2 Recording AEs Throughout the study, all identified adverse events (serious and non-serious) will be recorded on all appropriate source document and adverse event case report forms regardless of their severity or relation to the study.

A complete description of all adverse events will include event description, time of onset, investigator assessment of severity, relationship to study agent(s) or procedures/intervention(s), time of resolution/stabilization of the event, expectedness, determination of whether the AE qualifies as a SAE, and action taken. A change in the severity of the AE will also be documented. The PI will document assessment of severity and relationship on the source documents or the on the CRF.

10.2.2.3 Recording SAEs Serious adverse events will be recorded on the serious adverse event case report form and will include a narrative of the event signed and dated by the Principal Investigator and the Independent Safety Monitor.

10.2.2.4 Managing Adverse Events The site investigator must apply his or her clinical judgment as to whether an AE is of sufficient severity to require that the participant immediately be removed from further treatment under the protocol. The investigator must institute any necessary medical therapy to protect a participant from any immediate risk.

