10.2.3.2 Definition of Attribution The attribution of an adverse event to the study will initially be determined by the Principal Investigator or designated physician co/sub-investigator. The Principal Investigator or designee will record the determination of attribution on the appropriate adverse event or serious adverse event form. The attribution of an adverse event to the investigational drug(s) or other study drug (s) will be determined using the descriptors in the following table.

For the purpose of this study, in addition to all study medications, the following interventions/procedures will be considered when determining attribution:

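### Section 6.3.1.2.7 has parents log supplement-related adverse events, which conflicts with the all-event rule in 10.2.2 and may leave events on Days 1–14 unrecorded

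*Combined protocol and SAP*

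**What the plan says.** Section 6.3.1.2.7 is in the list of how each secondary objective is measured. It reads: "Supplement-related adverse events will be recorded by parents in a health log, in consultation with the study team and PI". It serves the secondary endpoint in 3.1.2, "The occurrence of supplement-related adverse events".

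Other sections set a wider scope:

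- Section 6.3.2: "Safety assessments will include parent-reported adverse events as described in Section 10.2". There is no relatedness condition.
- Section 10.2.2.1: "Any adverse event that occurs from the moment the participant has signed the consent form will be recorded and is reportable". It lists four routes of discovery, one of which is "Questioning the participant with standardized questions/procedures".
- Section 10.2.2.2 wants identified events "recorded on all appropriate source document and adverse event case report forms regardless of their severity or relation to the study".
- Section 10.2.3.2: "The attribution of an adverse event to the study will initially be determined by the Principal Investigator or designated physician co/sub-investigator".
- Section 6.4.2 asks parents to report any adverse event in Days 15–28. Section 6.4.1, which covers Days 1–14, lists dosing, stool collection and questionnaires and gives no adverse event instruction.
- Table 1 has an adverse event reporting row from Day 1 to Day 28 but does not define its scope.

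In 9.2.3 a treatment-emergent event is defined by its timing or worsening relative to the first dose, not by relatedness. These events are summarised as frequencies and percentages by arm. The Fisher test named in that section covers serious events and events that lead to withholding or discontinuing product.

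**The concern.** The health log is the one parent instrument that the protocol names for adverse events. If it is filled as 6.3.1.2.7 describes, someone must decide that an event is supplement-related before it is written down. Section 10.2 works the other way round: record first, attribute afterwards.

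The order matters because the protocol sets a demanding standard for calling an event unrelated. Under 10.2.3.2.2 the product is always suspect, and the unrelated category needs an indisputable or likely alternative explanation. A parent cannot be expected to apply that standard. Section 7.2.1 expects mainly gastrointestinal effects, yet 10.2.3.1 also gives grading scales for cough, fever and bronchospasm. A parent may well not connect those with a probiotic powder and so leave them out. Attribution codes 1 and 2 (unrelated and unlikely) can be given only to events that reach the investigator.

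At stake is the completeness of the treatment-emergent tables by arm and of the material for safety review, including any signal not expected from this product.

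**Working it through.** **Is there a figure to reproduce?** No. The documents give no adverse event rate and no rate of parental reporting. The check is a comparison of sections, a count of days, and an illustration on assumed figures.

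**Step 1: order of judgement.**

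| Section | What enters the record | Who judges relatedness, and when |
|---|---|---|
| 6.3.1.2.7 | Events already called supplement-related | Before entry; parents, consulting the study team and investigator |
| 6.3.2 | Parent-reported events, under 10.2 | Not stated here |
| 6.4.2 (Days 15–28) | Any event | Not stated here |
| 10.2.2.1 and 10.2.2.2 | Any event from consent, whatever its relation | After recording |
| 10.2.3.2 | – | Investigator or designated physician |

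The first row cannot be followed literally together with the last two.

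**Step 2: days exposed.** Supplementation lasts 14 days (section 3, Table 1). Table 1 places visits within that period on Days 7 and 14. Days without a scheduled visit: 14 − 2 = 12, and 12/14 = 86% of the supplementation period. Section 6.3.1.2.6 mentions weekly visits; an added Day 21 visit would fall outside Days 1–14 and leave the count unchanged. Days 15–28 are not counted, because 6.4.2 already asks for any event then. Twelve is an upper bound on the days on which the narrow wording could act. It is not a count of lost events.

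**Step 3: other sources on those days.** The daily stooling log (6.3.1.2.2) captures frequency, consistency, mucus and gross blood without regard to relatedness, so diarrhoea or constipation would leave a trace there. The named questionnaires cover reflux, sleep, feeding and stool. None is described as an adverse event questionnaire, and no section says that log entries are screened for adverse events.

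**Step 4: analyses exposed.** The treatment-emergent tables in 9.2.3 carry no relatedness condition, so they depend on all-cause capture. The Fisher test named there covers a narrower set of events.

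**Step 5: illustration on assumed figures.** Take 25 infants per arm (section 3). Assume true proportions with at least one event of 70% and 30%, and the same captured fraction c of affected infants in both arms, as blinding would suggest. Expected counts are 25 × p × c, and the observed difference is c × (0.70 − 0.30).

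| c | Expected infants with an event, by arm | Observed difference |
|---|---|---|
| 1.00 | 17.5 vs 7.5 | 0.40 |
| 0.75 | 13.1 vs 5.6 | 0.30 |
| 0.50 | 8.8 vs 3.8 | 0.20 |
| 0.25 | 4.4 vs 1.9 | 0.10 |

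With assumed proportions of 60% and 40%, the difference falls from 0.20 to 0.15, 0.10 and 0.05. Equal under-capture shrinks a real difference and does not create one. The values of p and c are assumptions, and low values of c would need the other capture routes to fail as well.

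**The case against.** The strongest reply is that 6.3.1.2.7 states how one endpoint is recorded and does not set the scope of safety capture. It sits among the secondary measures, matches the endpoint in 3.1.2, and is followed at once by 6.3.2, which sends parent-reported events to Section 10.2 without a filter. Section 10.2.2.1 then requires any event and lists standardised questioning, which can recover something that a parent did not write down. This stands in part. It makes the problem a conflict of wording with a possible loss, and not a demonstrated loss. It does not settle what parents are told to write on Days 1–14.

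A reader might infer more than the documents support:

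- **That parents are told to log nothing but related events, and decide relatedness themselves.** The sentence contains no such restriction, the log form is not in the documents, the log is kept in consultation with the study team and investigator, and formal attribution is the investigator's.
- **That 25 of 28 post-baseline days are exposed (28 − 3 visits; 89%).** Section 6.4.2 removes Days 15–28, which leaves at most 12 days.
- **That the Fisher comparison of all-cause events is undermined.** Section 9.2.3 names no test for all treatment-emergent events. Section 9.2.2 does provide categorical tests for case report form data in general, and 10.2.2.4 links stopping of product to adverse events, so a tested event could begin with a parent's report. Neither shows that such events would be missed.
- **That the arms would be biased against each other.** Section 3 blinds participants and staff, and nothing in the documents suggests that filtering would differ by arm.

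**Conclusion.** The point holds as an inconsistency with a bounded practical risk. Section 6.3.1.2.7, followed literally, contradicts 10.2.2 on what is recorded and 10.2.3.2 on who judges relatedness. No section expressly closes the gap for parents during supplementation.

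The possible consequence is under-counting in the descriptive treatment-emergent tables, confined to events that start on up to 12 of 14 days, that a parent thinks unrelated, and that no other route in 10.2.2.1 picks up. How many events meet all three conditions is unknown. The 12-day bound rests on the Table 1 visits being kept and on 6.4.2 being applied as written from Day 15. The absence of demonstrated bias between arms rests on the blind being maintained.

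**What to change.** Reword 6.3.1.2.7, and the health log to match, so that parents record every adverse event or health change from consent to Day 28 without judging its cause. State that the blinded investigator, or the designated physician, assigns relatedness under 10.2.3.2. Define the secondary endpoint in 3.1.2 as events given attribution code 3, 4 or 5 (possible, probable or definite). Add the same all-event instruction to 6.4.1, so that Days 1–14 match what 6.4.2 already says for Days 15–28.

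The cost is a wording change in the protocol and log and somewhat more entries for the investigator to review. The supplement-related endpoint is kept. The change is best made before data collection, because an event that was never logged may not be recoverable later.

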6.3.2 Safety and Other Exploratory Assessments

Safety assessments will include parent-reported adverse events as described in Section 10.2.

6.3.2.1 Stool Sample Collection

In addition to being used for hemoccult testing, infant stool specimens will be analyzed as an exploratory objective of the study and will be collected once during the Baseline period and daily (when available) for Days 1-14, 21, and 28, and assessments may include the following markers:

- Fecal calprotectin levels
- Fecal pH levels
- Fecal metabolomics
- Markers of inflammation and enteric cytokines including, but not limited to, IL-1, IL-8 and TNF-alpha
- Levels of eosinophil-related granular proteins
- Intestinal permeability/integrity markers including, but not limited to, lipocalin (NGAL)

6.3.3 Stool Sample Documentation, Training, Storage, and Handling

6.3.3.1 Baseline Samples

Baseline stool swabs and chunks of stool must be collected before the first study supplementation is consumed. After collection, the parents will store the swab tubes (white top tube) at room temperature and will store the chunk tubes (brown top tube) in their home freezer in a bag provided to retain those samples. At the Day 7 in-person Study Visit, parents will bring all Days 0-7 stool samples (swab, chunk, and card) with them to the visit. At the end of the study, parents will bring all remaining stool samples to the study site at the Day 28 End of Study in-person Visit. All efforts should be made to collect stool samples within the target collection windows. Parents will be trained on how to collect the samples at enrollment and as needed throughout the study.

6.3.3.2 Stool Swabs

Starting with a freshly soiled diaper, the parent will first collect the stool swab sample using the supplies provided in the stool collection kit (green-topped tube containing a buffer/bead mixture and packaged swab). Parents will swab their infant's soiled diaper, collecting enough sample to entirely coat the head of the swab. They will place the stool-covered swab into a white-topped collection tube containing stabilization buffer and will snap the swab head off at the breakpoint, leaving the swab head in the tube. They will seal the tube and shake vigorously to ensure distribution of the stool within the stabilization buffer. Swab-containing tubes (white cap tube) will be stored at room temperature. .

6.3.3.3 Stool Chunks

Using the supplies provided in the stool collection kit (empty snap-cap tubes and white stool collection spatulas), mothers will collect as much loose stool sample from their infant's soiled diaper as possible before snapping the lid tightly closed for storage. They will likely need to take multiple scoops to fill the tube as much as possible. If little stool is available for collection in a particular diaper, mothers will be instructed to use subsequent soiled diapers that fall within the same stool collection window to add to the already frozen snap-cap tube.

For example: A mother can only collect the swab tube and a very small spatula-full of stool for the stool 'chunk' sample. If baby stools later within the same stool collection window, the mother will remove the previously frozen partial 'chunk' sample tube(s) from the freezer, add as much stool as possible and re-freeze the entire sample. She will not need to prepare a second swab sample and should not try to add more material to the green-topped tube.

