6.3.3.5 Stool Sample Analysis

DNA and RNA will be extracted from stool swab samples and will be used for shotgun sequencing, next generation sequencing, and/or quantitative PCR to determine levels of *B. infantis*, total Bifidobacterium, microbial signatures, and relative abundance of the most abundant bacterial taxa. Biochemical analyses may be performed on stool chunk samples to evaluate markers as described in Section 6.3.2.

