6.6.3 Stool Collection

Stool samples will be collected from the participants at the following time points:

- At Screening / Baseline
- Day 3 (within a window of Study Day 3-5)
- Day 14 (+/- 1 day)
- Day 28 (+/- 1 day)

The stool samples will be banked and used for 16s rRNA or metagenomic sequencing for microbiome evaluation and biologic studies.

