9.2.3 Efficacy Analysis

Primary Endpoint(s) The primary objective of the study is to assess the effectiveness of the probiotic, *B. infantis* INF108F, on modulating the gut microbiome composition of breastfed infants diagnosed with FPIAP from Baseline to Day 28, including colonization of INF108F. This will be measured using stool 16S analysis and quantitative PCR. Treatments will be compared using a Wilcoxon Rank Sum test.

Secondary Endpoint(s) The secondary objectives of this study as measured:

- Evaluating the reduction in stool frequency and improvement of stool consistency by Day 7 using Questionnaire
- Evaluating the improvement of infant GER symptoms by Day 14 using Questionnaire. Reduction by 50 percent from Baseline to Day 14 Infants with a reduction in the number of crying/fussing episodes of greater than or equal to 50 percent on Day 14 will be counted as a success. The number of successes per treatment group will be compared using a Chi-square or Fisher's Exact test, as appropriate.
- Evaluating the improvement of feeding difficulties by Day 14, using Questionnaire. The number of successes per treatment group will be compared using a Chi-square or Fisher's Exact test, as appropriate.

- Evaluating the improvement of infant's sleep by Day 14, using Questionnaire.
- Changes of stool cytokine profile by Day 28. The changes from baseline to Day 28 will be compared for the two groups using a repeated measures ANOVA.

Safety Analysis Fisher's Exact Test will also be used to compare treatment groups for SAEs and AEs resulting in withholding or discontinuing the study products. Adverse events will be summarized. Frequencies and percentages of subjects with treatment-emergent adverse events (TEAEs), serious TEAEs and TEAEs causing premature discontinuation will be provided by treatment group. An AE is treatment emergent if it 1) occurs after the first dose of randomized study treatment or 2) if it is present prior to receipt of randomized study treatment but worsens in severity or increases in frequency after the first dose of randomized study treatment.

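### Topping up and re-freezing stool tubes at home gives the biomarker samples a varying, unrecorded thaw and pooling history that may differ by arm

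*Combined protocol and SAP*

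**What the plan says.** Each collection yields a swab in stabilization buffer, kept at room temperature, and a chunk tube, kept in the home freezer.

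- **Trigger for a top-up (6.3.3.3).** "If little stool is available for collection in a particular diaper, mothers will be instructed to use subsequent soiled diapers" from the same window.
- **Procedure (6.3.3.3).** The worked example is conditional: "If baby stools later within the same stool collection window", the mother is to "remove the previously frozen partial 'chunk' sample tube(s) from the freezer, add as much stool as possible and re-freeze the entire sample".
- **Swab (6.3.3.3).** The swab is left alone: "She will not need to prepare a second swab sample and should not try to add more material to the green-topped tube".
- **Use of the specimens (6.3.3.5).** For sequencing and PCR, "DNA and RNA will be extracted from stool swab samples". For the rest, "Biochemical analyses may be performed on stool chunk samples to evaluate markers as described in Section 6.3.2". Section 6.3.2.1 lists those markers: calprotectin, pH, metabolomics, inflammatory markers and cytokines, eosinophil granule proteins, and permeability markers such as lipocalin.
- **Status of the markers.** Section 3.1.3 classes all of them as exploratory. Section 9.2.3 nevertheless lists "Changes of stool cytokine profile by Day 28" among the secondary analyses, compared by repeated measures ANOVA.
- **Collection window.** Sections 6.3.2.1 and 6.4.1 describe daily collection over Days 1-14. Section 6.6.3 instead gives "Day 3 (within a window of Study Day 3-5"), then Day 14 and Day 28, each with one day either side.

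**The concern.** Some chunk tubes will be frozen once and hold one diaper. Others will have been taken out, warmed to some degree by fresh stool, and frozen again, possibly more than once. The plan sets no limit on the number of top-ups or on time out of the freezer. It does not ask for either to be noted: the stooling log in 6.3.1.2.2 covers frequency, consistency, night stooling, mucus and gross blood only. An affected tube could not be identified later, so the analysis could neither adjust for it nor exclude it.

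Handling is also linked to what happens after randomization. Whether a top-up is possible depends on how often the infant stools, and stool frequency is a secondary endpoint (3.1.2) that 9.2.3 hopes to see reduced. Stool consistency, also expected to improve, may affect how much can be collected from a diaper; that link is an inference. Randomization balances the handling of the baseline sample, but not of the later ones. At stake are the marker comparisons between arms and the matching of each marker value to its swab.

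**Working it through.** The plan gives no figure for the share of tubes topped up, for stool rates, or for the effect of a thaw on any marker. There is no stated number to reproduce, so the check covers the direction that the rule implies and then what would be needed to size it.

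**1. Conditions for a top-up.** Both are in 6.3.3.3: (a) the first diaper yields little stool; (b) at least one more stool follows in the same window. An infant with a single stool in the window cannot be topped up.

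**2. Direction.** Let s be the probability that the first stool is too small, and let the number of stools N in a window of w days be Poisson with mean λw, where λ is stools per day. Given that a sample was obtained,

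P(top-up) = s × P(N ≥ 2 | N ≥ 1) = s × [1 − e^(−λw)(1 + λw)] / [1 − e^(−λw)].

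Both s and λ are assumptions. For λ = 1, w = 1, s = 0.3: 0.3 × (1 − 0.736)/(1 − 0.368) = 0.3 × 0.418 = 0.125. The full set at s = 0.3:

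| Stools per day | 0.5 | 1 | 2 | 4 | 8 |
|---|---|---|---|---|---|
| 1-day window | 0.069 | 0.125 | 0.206 | 0.278 | 0.299 |
| 3-day window | 0.171 | 0.253 | 0.296 | 0.300 | 0.300 |

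The pattern is the same at s = 0.1 and s = 0.5. If stool size is unrelated to frequency, top-ups rise with frequency or level off.

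**3. What would reverse it.** For an infant at 1 stool a day to be topped up as often as one at 4 a day, small first stools would have to be 2.2 times as likely with a 1-day window (0.925/0.418), or 1.2 times with a 3-day window. The documents give nothing on this, so the sign is open.

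**4. Size, by assumption only.** The shift between arms is (difference in top-up share) × (shift per top-up). Assume 2 versus 4 stools a day and a 20% shift per top-up.

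- 1-day window, s = 0.1, 0.3, 0.5: (0.093 − 0.069) × 0.20 = 0.5%; (0.278 − 0.206) × 0.20 = 1.4%; (0.463 − 0.343) × 0.20 = 2.4%.
- 3-day window, s = 0.3: (0.300 − 0.296) × 0.20 = 0.1%.
- If instead s = 0.5 in the arm at 2 a day and 0.3 in the arm at 4 a day (1-day window): (0.343 − 0.278) × 0.20 = 1.3%, with the opposite sign.

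Under the same assumption, mixing topped-up and once-frozen tubes within an arm adds scatter with SD √[p(1 − p)] × 0.20. At p = 0.206 this is 8%, and at p = 0.278 it is 9%, of the marker level. On these inputs the added scatter exceeds the bias. No marker SD is given, so neither can be set against ordinary variation.

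**5. Pooling interval.** Under 6.6.3, a tube begun on Day 3 and topped up on Day 5 spans 5 − 3 = 2 days; the windows of one day either side also span 2 days. Under the daily schedule of 6.3.2.1, pooling stays within about one day. Which applies is not settled. Section 1.4 says the microbiome changes within days of starting the supplement, so a two-day pool at the early time point matters more than one at Day 28.

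**The case against.** The strongest case against is that the damage is limited and unproven. The primary endpoint rests on swabs that are never topped up. The marker assays are worded as optional in 6.3.3.5 and are exploratory in 3.1.3. The documents contain no stability data, so it is not shown that one re-freeze changes any of these markers; even the thaw is inferred from removal, addition of fresh stool and re-freezing. All of this stands, and it limits the weight of the point.

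A reader might go further and infer that thawing happens most often in infants who stool least, and therefore more often in the active arm if the product lowers stool frequency. The documents do not support that. The trigger is the amount in one diaper, which is not an endpoint, and a further stool is required. On the rule alone, a less frequent stooler would tend to have fewer top-ups.

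It is also fair to object to making the first-diaper tube the only specimen. Infants with small stools would then lack material, and 9.2.2 rules out imputation, so missing data would depend on stool volume after randomization. The fix below avoids this.

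What the objections do not answer is that the handling varies, is tied in part to a trial outcome, and leaves no record.

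**Conclusion.** The point holds as a correctable weakness in specimen handling for the biomarker analyses. Chunk tubes will differ in freeze-thaw cycles and in diapers pooled, the plan leaves no trace of which differ, and a topped-up tube no longer matches its swab. Bias between arms is possible in either direction. The more likely harm is extra scatter, with about 40 completers in all (50 × 0.8), or 20 per arm. The percentages in the working rest on assumed stool rates, an assumed share of small stools and an assumed 20% shift; they illustrate the mechanism and do not estimate it. The conclusion also assumes that re-freezing or pooling affects at least some of the markers. The primary endpoint is not touched. The change is worth making before collection, because the history of a tube cannot be recovered afterwards.

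**What to change.** 1. In 6.3.3.3, replace the top-up instruction. A frozen chunk tube is not re-opened; later stool from the same window goes into a second empty snap-cap tube, labelled with date and time and frozen separately.
2. In 6.3.3.5, let the laboratory combine tubes from one window at a single thaw when the first holds too little, and record which samples were combined.
3. In 9.2.3, add a sensitivity analysis of the chunk-based markers restricted to single-diaper samples.
4. State the collection window once, reconciling 6.3.2.1 and 6.4.1 with 6.6.3, and give stool cytokines one status across 3.1.3 and 9.2.3.

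The cost is one extra tube per window in the kit, slightly more labelling for parents, and a field in the laboratory record. No stool volume is lost, because tubes can still be combined. Sample size, alpha and the primary analysis do not change.
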